## 2) Objectives

- 1. Assess safety and tolerability of metformin in individuals with FXS ages 6 to 35 who are treated over a 4-month period (and an additional 2 years if they participate in the open label extension).
- 2. Assess the benefit of metformin in the treatment of language deficits, behavior problems, and obesity/excessive appetite in individuals with FXS over a 4-month period (and an additional 2 years if they participate in the open label extension).
- 3. Assess the utility of innovative outcome measures, including measures of brain processing (event related potential habituation paradigm and social gaze monitoring using the Tobii Eye Tracker), language/cognitive measures (NIH Toolbox cognitive battery measures and expressive language sampling), a measure of memory (The Memory Game), behavioral and quality of life measures [Aberrant Behavioral Checklist–Community (ABC-C) fragile X version, Child Sleep Habits Questionnaire (CSHQ), Anxiety Depression and Mood Scale (ADAMS) Swanson, Nolan and Pelham questionnaire (SNAP-IV), and Pediatric Quality of Life Questionnaire (PedsQL) Parent Proxy], EuroQol-5D (EQ-5D-3L or EQ-5D-Y), Sensory Profile-2 (up to 15 years old) or Sensory Profile Adolescents/Adults (11 years and older), and Care Related Quality of Life (CarerQoL)], a food questionnaire (Automated Self-Administered 24-Hour Dietary Assessment Tool (ASA24)), in addition to standard measures of outcome [Clinical Global Impression Scale-Severity (CGI-S), Clinical Global Impression Scale-Improvement (CGI-I), Visual Analog Scales (VAS), and Vineland

- Adaptive Behavior Scales-Third Edition (for English speakers) and Second Edition for French speakers)].
- 4. Assess molecular biomarkers that may predict which patients may be likely to benefit from metformin treatment. A panel of molecular biomarkers, including FMRP level, MMP9, S6 Kinase, EIF4E, *CYFIP1* mRNA, CYP450 allelic variants, and metabolome variants, genomic variants, proteomics and mRNA sequencing will be studied.

## 3) Background

FXS is the leading monogenic cause of intellectual disability and autism spectrum disorder. Treatment for FXS is currently non-pharmacological or symptomatic interventions. FXS is associated with an increase in body mass index (McLennan et al., 2011), and a subgroup of patients with FXS develops severe hyperphagia, obesity, and hypogonadism or delayed puberty. This presentation has been described as the Prader-Willi phenotype of FXS (PWP) (Nowicki et al., 2007), as it is similar to those with the Prader-Willi syndrome caused by a deletion at 15q11-q13. Unlike Prader-Willi syndrome, the FXS-PWP does not have a deletion of 15q11-q13 or chromosome 15 maternal uniparental disomy (McLennan et al., 2011). However, *FMR1* protein (FMRP) binds to cytoplasmic interacting *FMR1* protein (CYFIP1), a protein that affects synaptic remodeling, including FMRP protein translation (Schenck et al., 2001); CYFIP1 is localized to 15q, the critical region in Prader-Willi-syndrome (Chai et al., 2003). The level of CYFIP1 mRNA expression has been found to be lower in those with the PWP compared to FXS without the PWP (Nowicki et al., 2007), so this appears to be a molecular correlate of the obesity in the PWP. One of the biomarkers to be evaluated in this proposal will be CYFIP1 mRNA expression levels that may change with metformin treatment in those with or without the PWP of FXS.

Metformin is a type 2 diabetes medication that can also improve obesity and excessive appetite. The Food and Drug Administration approved metformin for its effects in lowering blood glucose levels in patients with noninsulin-dependent, type 2 diabetes. Some studies report minimal to moderate decrease in weight in groups of patients with insulin resistance (Klein et al., 2006). Metformin has been shown to be effective and safe in decreasing weight gain associated with atypical antipsychotic use and is well tolerated by children and adolescents with ASD aged 6-17 years old, with up to 500mg twice daily for children aged 6-9 years and 850 mg twice daily for those 10-17 years old (Anagnostou et al., 2016). It has also been utilized for the treatment of obese children and adults who do not have type 2 diabetes with a short-term reduction in BMI (Park et al., 2009; Klein et al., 2006). Metformin is also effective in glycemic control in patients who are not obese (Ong et al., 2006). There is little to no risk of hypoglycemic episodes in the use of metformin because its mechanism of action does not directly stimulate insulin (Bolen et al., 2007; Bodmer et al., 2008).

Metformin has emerged as a candidate drug for the targeted treatment of FXS based on animal studies showing rescue in the FXS model (Monyak et al., 2016; Weisz et al., 2015; Gantois et al., 2017). The fly, Drosophila melanogaster, has a homologue of *FMR1* called dfmr1. The Drosophila FXS model has shown that drosophila insulin-like peptide 2 (Dilp2) in insulin-producing cells results in elevated insulin signaling via the PI3K/Akt/mTOR pathway. The dysregulated insulin signaling in this fly model of FXS leads to defects in circadian rhythm and short- and long-term memory deficits. Use of metformin in this study had been able to rescue and restore memory deficits (Monyak et al., 2016). Further studies performed in the Sonenberg lab (Gantois et al., 2017) showed that adult treatment in the FXS knock-out mouse rescued multiple phenotypes, including social novelty, grooming, dendritic spine morphology, and electrophysiology in eCA1 of the hippocampus. Metformin may contribute to normalizing signaling pathways in FXS in the central nervous system, which may include activities of ERK, mTOR and PI3K, which have shown to be pathogenically overactive in FXS.

In addition, metformin inhibits phosphodiesterase, which would lead to correction of cAMP levels. Moreover, metformin inhibits MMP9 production, which is also elevated in FXS (Hoeffer et al., 2012; Muzar et al., 2016; Dziembowska et al., 2013), and MMP9 as a biomarker will be assessed in this proposal. Looking at the potential signaling pathways, metformin appears to be a good candidate for targeting several of the intracellular functions in neurons disrupted in FXS and therefore possibly rescuing several types of symptoms in individuals with FXS.

[name] team (MIND Institute) has utilized metformin in the clinical treatment of over 20 individuals with FXS between the ages of 4 and 58 years and have found benefits not only in lowering weight gain and normalizing appetite, but also in language and behavior with doses up to 1000 mg twice a day (Dy et al., 2017). [name] team has recently reported in Dy et al. (2017) the details of the first 7 patients treated clinically for whom pre and post Aberrant Behavior Checklist results were obtained and documented improvement in weight, language, and behavior. This medication has been well tolerated, even in the 4-year-old patient with FXS, and it is time now to carry out a controlled trial.

Considering these promising preliminary results and the established safety of metformin in children, we propose to carry out a randomized, placebo-controlled trial of metformin to further assess safety and benefits in the areas of language/cognition, eating, and overall behavior, in addition to weight loss. The trial will include a US site at the MIND Institute and two Canadian centers (University of Alberta and CHU Sainte-Justine).

This study also provides an opportunity to carry out novel outcome measures that are capable of documenting improvements in the processing of information in the CNS (event related potentials (ERPs) and Tobii eye tracking), cognitive abilities (NIH Toolbox cognitive battery measures and expressive language sampling), critical biomarkers of involvement by the *FMR1* 

mutation (CGG repeats, degree of methylation, and FMRP expression levels), and neurochemical changes in the CNS that can also be measured in blood and fibroblasts (MMP9, S6K, EiF4E, and CYFIP1). Finally, the cytochrome P450 (CYP) isozymes, highly polymorphic drug-metabolizing enzymes, have been demonstrated to be responsible for the metabolism of metformin in humans, mainly via CYP2C11, 2D1, and 3A1/2 (Choi and Lee, 2006). Thus, in this study we will assess if the CYP450 allelic variant genotypes involved in the metformin pharmacokinetics determine the efficiency of response to metformin. Since metformin absorption is done by active transport via the organic cation transport (OCT), we will also assess polymorphism in that gene.

Leveraging the current RCT program and adding an open label extension. New information pointing toward the importance of considering a metformin open-label extension to our current randomized control trial of metformin in individuals with Fragile X syndrome (FXS) has emerged for several reasons. We are therefore adding a 2 year (24 months) optional extension of open-label metformin trial to all participants of our approved RCT of metformin in FXS.

Rationale: 1) Based on reports from open-label trial papers from [name] group suggesting potential improvements in development, testicular size, and IQ in 11 patients with FXS, there are important long term tolerance and effects that need to be documented at the end of our controlled trial should the patients continue on an open-label treatment of metformin. 2) We know that metformin is well tolerated during short term treatments in a majority of individuals with FXS (from our RCT participants in Edmonton and at UC Davis). This supports the initial results observed in individuals with ASD ([name] trial). In addition, a recent open label trial in Sherbrooke (QC) by [name] identified no adverse event and pointed toward the need for longer treatment (personal communication, paper in preparation). 3) There is a strong demand for an extension from families involved so far in our trial at all sites. Previous RCTs in fragile X were also followed by open labels in part because there was a strong demand from families who knew that they had a 50% chance of not receiving the active molecule (e.g. the NIH supported the Neuro NExt trial testing the effect of AFQ056 in a new combined paradigm (PI: [name]) which also includes an open-label extension). 4) Importantly, adding the open-label extension to the trial allows significant cost-saving compared to a stand-alone project. Indeed, database, server, biobank, and pharmacy cost are not duplicated in this design.

Scientific Merit: In addition to allowing all participants to have a chance to assess the effect of metformin, the extension would allow us to: 1) Evaluate potential variation in the long-term effect of metformin, particularly on cognition, which is the most important issue for the families. For instance from visit 1 to visit 3, we will measure potential change on the impact of metformin long-term treatment on our primary outcome measure (expressive language sampling), but also activity of daily living abilities (as measured by Vineland and IQ). 2) Leverage the baseline measures of psychological and biological biomarkers for all participants. This means that every participant will have the opportunity to be on metformin at some point in the trial within a

monitored framework and all patients will have baseline measures (from visit 1 of the RCT) which can be used as internal control. This is very important as most families want to test the effect on their children and will do so outside of the investigational framework if it is not made available to them. Some families will get it prescribed by their general practitioner for instance. This will lead to significant loss of data. 3) Provide additional longitudinal data on cognitive development, functional performance, the health economics and quality of life for individuals and families with fragile X syndrome with metformin. 4) Provide additional longitudinal biological samples (including brain activity) for each given individual with FXS at 1 and 2 years, allowing for a better understanding of potential changes in biomarkers over time. This would make the dataset unique and very useful in integrating the developmental origin of disease concept to the study of FXS.

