### 5) Study Timelines

The study plans to enroll 60 participants over a 3-year period at each site. Approximately 20 patients per year with FXS will be randomized at each site to receive either metformin or placebo for a 4-month period. During the 4-month study period, subjects will attend three visits to the recruiting site: screening/baseline, 2-month, and 4-month visits. In addition, routine phone calls will be made once per week during the first month of the study, with the week 4 phone call being conducted by the study physician, and once at week 12/month 3.

Extension Visit schedule: Informed consent will be obtained either concomitantly to visit 3 of the original schedule of the RCT portion or later if the participant finished the RCT already, but would like to enter the open-label extension. A follow up in-person visit will be done at 1 year of the open-label trial, or before if needed, and another in-person visit will occur at 2 years. Scheduled follow up phone calls will be done weekly for the first month of the extension and then every 4 months. If a participant begins the extension study within 1 year of ending the RCT portion of the study, Visit 3 of the RCT will be considered to be Visit 1 of the extension and the participant would be seen at a 1 year follow up from when they had their Visit 3 of the RCT portion. Those participants previously enrolled in the RCT who have been taking metformin off-label for more than a year can be enrolled in the extension phase. These participants will have a 'first visit' for the extension phase in addition to the previously-completed third visit for the RCT (as that visit occurred more than a year before starting the extension phase). Informed consent will be obtained at this 'first visit'.

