# 6) Study Endpoints

The primary outcome measure will be the Expressive Language Sampling (ELS) measure which is conducted at baseline and at the end of treatment, as described in detail in Section 7. The ADOS-2 and Leiter-III will be administered at baseline only for purposes of study population characterization and will not be repeated as outcome measures. All other measures will be secondary outcome measures and are also described in detail in Section 7. Attempts will be made to administer all secondary measures for each participant, to the extent his or her cognitive age and ability allows. Safety endpoints will include safety blood draws and physical exams at each study visits.

For the extension, the primary outcome measure will remain the Expressive language sampling (ELS) measured at the 1 year and 2 year visits. This will provide a connection with the RCT primary outcome. The extension secondary outcome measures will be measured at the 1 year and 2 year visits and will include: Leiter IQ test, Vineland (version 3 for English and version 2 for French), Memory Game (online), NIH Toolbox, CarerQol-Quality of life questionnaires (online), EQ-5D- Health economics questionnaires (online), Pediatric Quality of Life (PedsQL) Parent

Proxy Questionnaire (online), Aberrant Behavior Checklist–Community (ABC-C) (online), Visual Analogue Scale (VAS) (online), Swanson, Nolan and Pelham Questionnaire (SNAP-IV) (online), Clinical Global Impression Scale–Improvement (CGI-I) (online), Anxiety Depression and Mood Scale (ADAMS) (online), Sensory Profile-2 or Sensory Profile Adolescent/Adult, Child Sleep Habits Questionnaire (CSHQ) (online), Automated Self-Administered 24-Hour Dietary Assessment Tool (ASA24), biological biomarkers (blood, stool, and urine), resting EEG and event related potentials (ERPs), and eye tracking.

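### The open-label extension has no concurrent control and no specified analysis, and the only comparator it names, each participant's own RCT Visit 1, cannot separate long-term metformin effect from development and off-drug time

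*Combined protocol and SAP*

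**What the plan says.** Section 2 sets the aim: "Assess the benefit of metformin in the treatment of language deficits, behavior problems, and obesity/excessive appetite in individuals with FXS". The aim applies to the randomised phase and, for those who join it, to both years of the extension. Section 3 describes a "2 year (24 months) optional extension of open-label metformin trial to all participants of our approved RCT", so everyone in the extension takes metformin. Section 6 states that "the primary outcome measure will remain the Expressive language sampling (ELS) measured at the 1 year and 2 year visits".

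The comparator appears only in the Scientific Merit paragraph of Section 3: "all patients will have baseline measures (from visit 1 of the RCT) which can be used as internal control". The same paragraph says that "from visit 1 to visit 3, we will measure potential change on the impact of metformin long-term treatment on our primary outcome measure", without saying whether these are RCT or extension visits.

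Section 5 and the first footnote to the schedule table in Section 7 treat RCT Visit 3 as extension Visit 1 for anyone entering within a year, and time the 1-year visit from it. Section 5 also admits former RCT participants "who have been taking metformin off-label for more than a year can be enrolled in the extension phase"; they have a separate first extension visit, and Section 7 lets off-label users skip the dose ramp-up.

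The efficacy analysis in Section 8 is an ANCOVA of the 4-month language outcome. It gives no baseline, model, age adjustment or by-arm comparison for the extension. The only added controls are stool donors without fragile X syndrome (Sections 4 and 7).

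**The concern.** A within-person change is a treatment effect only if nothing else would have moved the outcome. Participants enter from age 6, and the primary outcome is a count of different words. Section 7 adjusts it for talkativeness but states no age adjustment. Some gain from development over more than two years is plausible in the younger participants whatever they take.

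RCT Visit 1 also means different things in different people. In the metformin arm it is the last value before first metformin. In the placebo arm it precedes first metformin by at least 16 weeks. In off-label users it is followed by more than a year of metformin outside the trial.

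A gain from RCT Visit 1 in language, Vineland or IQ could therefore be read as long-term benefit if the drug did nothing. For tolerability, new starters and people already known to tolerate the drug would be mixed unless tabulated apart.

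**Working it through.** The documents give no sample size, power or effect size for the extension, so there is no planned figure to reproduce.

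**Inputs.** RCT Visit 3 is at week 16, and extension visits are at weeks 52 and 104 (schedule table, Section 7). Minimum age is 6 and maximum 35 (Section 4). Allocation is 1:1 (Section 18). Dosing stops after RCT Visit 3 (Section 7).

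**Length of the interval.** RCT Visit 1 to the 2-year visit is 16 + 104 = 120 weeks, or 120/52 = 2.3 years. That is 2.3/6 = 38% of the age of the youngest entrant and 2.3/35 = 6.6% of the age of the oldest.

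**Off-drug share, placebo arm, no gap before the extension.**
- 1-year visit: 16/(16 + 52) = 16/68 = 24%.
- 2-year visit: 16/120 = 13%.

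**Off-drug share, placebo arm, with a gap of g weeks and no off-label metformin in it.** If visits run from RCT Visit 3, the shares are (16 + g)/68 and (16 + g)/120. The documents state this clock for the 1-year visit; for the 2-year visit it is an assumption.

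| g (weeks) | 1-year visit | 2-year visit |
|---|---|---|
| 0 | 24% | 13% |
| 26 | 42/68 = 62% | 42/120 = 35% |
| approaching 52 | 68/68 = 100% | 68/120 = 57% |

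The safety-laboratory text in Section 7 instead times 1 and 2 years from the start of the extension. If all visits ran that way, a gap approaching 52 weeks would give (16 + 52)/(16 + 52 + 52) = 57% at 1 year and 68/172 = 40% at 2 years. Any gap is also off-drug time in the metformin arm.

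**Development (assumed rates; the documents give none).** A drift of 0.05, 0.1 or 0.2 baseline SD per year over 2.3 years produces a change of 0.12, 0.23 or 0.46 SD with zero drug effect. For a paired t-test at two-sided 0.05, the noncentrality is √n × change/√(2(1 − r)). For assumed pre-post correlations r from 0.5 to 0.8, the proportion of trials giving a significant change would be:

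| Drift per year | n = 30 | n = 60 |
|---|---|---|
| 0.05 SD | 9–16% | 14–29% |
| 0.1 SD | 23–49% | 42–79% |
| 0.2 SD | 69–97% | 94–100% |

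The nominal rate is 5%.

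**Precision of the randomised alternative.** The 95% half-width for early versus delayed start, adjusted for baseline with assumed r = 0.5, is 1.96 × √((2/n)(1 − 0.25)). This is 0.31 SD at 60 per arm and 0.44 SD at 30 per arm.

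**The case against.** The strongest reply is that uncontrolled follow-up is inherent in an optional open-label extension, and that the text offers RCT Visit 1 as something that can be used, in a rationale paragraph. This is fair. A reader might infer that the sponsor plans to count development as drug effect, or to pool off-label users into the tolerability rate. No passage says either. What stands is the absence of any specified analysis, with one weak comparator named in its place.

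A second baseline also exists. RCT Visit 3 serves as extension Visit 1 for entry within a year and removes the placebo period. It does not remove development or a gap before entry. In the metformin arm it is already on drug. Leiter is not given at that visit at all.

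The outcome may be less vulnerable than it looks. Section 7 reports negligible practice effects for the word count, so practice is not a good argument against it. Vineland is described as normed and IQ is a standardised score, so raw growth may affect them less. Adults may drift little. These points limit the size of the bias, which is unknown, but supply no control.

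Finally, early versus delayed start is not a full answer: both arms take metformin in the extension, so a benefit reached quickly could leave no difference at 1 or 2 years. That limitation stands. The contrast still keeps the randomised allocation, which pre-post change does not use.

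**Conclusion.** The concern holds in a limited form. The extension is single-arm, its analysis is unspecified, and the one comparator named would mix metformin effect with at least 120 weeks of development and, in the placebo arm, at least 16 off-drug weeks (13% of the interval at 2 years, 24% at 1 year). The upper figures, about 57% and nearly 100%, assume entry close to a year after RCT Visit 3, no off-label use in the gap, and visits timed from RCT Visit 3. The false-positive rates rest wholly on assumed drift, correlation and numbers entering; they show sensitivity and are not a forecast.

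Long-term benefit under Objective 2 therefore cannot be attributed to metformin as planned. A reader might go further and conclude that it can never be addressed. The documents do not support that: allocation was randomised, and Section 15 keeps participants blind to arm until all procedures and analyses are complete, so a by-arm comparison remains possible. Nor does the point touch the 4-month randomised comparison or descriptive safety reporting.

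**What to change.** 1. Replace the internal-control sentence in Section 3 with a specified analysis: comparison by randomised arm (early versus delayed start) at the 1-year and 2-year visits, adjusted for RCT Visit 1 and age. State that pooled pre-post change is descriptive and does not support a claim of benefit.
2. Where within-person change is shown, use the last value before first metformin: RCT Visit 1 for the metformin arm; RCT Visit 3 for the placebo arm, or extension Visit 1 if entry is more than a year later without off-label use. For Leiter only RCT Visit 1 exists, so report it by arm.
3. Record actual metformin exposure, including off-label periods and gaps. Tabulate tolerability separately for new starters, RCT metformin-arm continuers and off-label continuers; the last two groups have both already shown some tolerance.
4. Reconcile the two clocks for the 1-year and 2-year visits (Section 5 and the schedule footnote against the safety-laboratory text in Section 7), and say which visits Section 3 means by 1 and 3.

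The cost is protocol wording, exposure dates and a few more tables, with no new visits, tests or participants. The downside is a less flattering result: the by-arm contrast covers only those who enter, differs by about 4 months of exposure, can miss a quickly reached benefit, and has the wide intervals shown above.
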